#### 7.10 Safety Analysis

All safety summaries will be based on the Safety Analysis Set. The safety analysis will use OC data and be restricted to descriptive statistics unless otherwise specified.

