The 8 week duration is sufficient to evaluate the efficacy because in all previous studies, a plateau in blood pressure reduction was observed after 4 weeks of treatment for both TAK-491 and valsartan. The study design employs a 3 to 4 week washout period to establish a true drug-free baseline blood pressure and to determine severity of hypertension in enrolled population at randomization. A coincident 2-week, single-blind, placebo run-in period is to evaluate study drug compliance. This short-term washout/placebo treatment period is not associated with increased risk of major irreversible cardiovascular events in a hypertensive population [14,15].

Frequent visits and withdrawal criteria for elevated BP during the study as defined in Section 7.5 will further ensure the safety of the study subjects.

The primary endpoint of this study is sitting, clinic SBP, which is a well-established measure for assessing antihypertensive effect and is a better predictor of cardiovascular outcomes than DBP. Clinic SBP is an appropriate primary endpoint because it is validated as a surrogate endpoint in observational and interventional clinical studies [16-18].

ABPM parameters will also be evaluated in a subset of approximately 60 patients per arm. ABPM parameters are clinically more predictive of cardiovascular outcome than clinic BP measurements, as demonstrated by numerous studies. In particular, mean 24-hour SBP is the best predictor of cardiovascular risk, even after adjustment for risk factors including clinic BP [19-21].

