13.1.1 Analysis Sets

All randomized subjects will comprise the randomized set. Analysis sets to be used include the following:

Safety Analysis Set: All subjects who receive at least 1 dose of double-blind study medication. Subjects will be analyzed according to the study medication they received.

Full Analysis Set (FAS): All randomized subjects who received at least 1 dose of study medication. Subjects will be analyzed according to the treatment group to which they were randomized.

Per-Protocol Set (PPS): All subjects in the FAS, excluding any subjects who had major protocol violations. Major violations from the protocol leading to exclusion from the Per Protocol Set will be identified prior to unblinding of subject's treatment assignment.

The FAS will be the primary data set used for efficacy analyses. Efficacy analysis based on the Per Protocol Set will also be performed where appropriate. All routine safety analysis will be based on the Safety Analysis Set.

All subjects who were randomized more than once will be excluded from the safety analysis set, the FAS, and the PPS.

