## 7.3 Analysis Sets

The following analysis sets will be used for analysis and presentation of the study data:

**The Randomized Set** will consist of all subjects who were randomized. For subjects who were randomized more than once, only the first randomization is used.

The Safety Analysis Set will consist of all subjects who received at least one dose of double-blind study medication. Subjects will be analyzed according to the study medication they received. Subjects who were randomized more than once are excluded from the Safety Analysis Set.

The Full Analysis Set (FAS) will consist of all randomized subjects who received at least one dose of double-blind study medication. A subject in FAS will be included in the analyses of a specific variable only when there is both a baseline value and at least one value during the double-blind treatment period. Subjects will be analyzed according to the treatment group to which they were randomized. Subjects who were randomized more than once are excluded from the Full Analysis Set.

The Per Protocol Set (PPS) will consist of all subjects in the FAS, excluding those who meet following criteria:

- 1. Subjects with SBP <150 mm Hg on Day 1.
- 2. Subjects who take study drug of a different treatment from the one randomized.
- 3. Subjects who are randomized more than once.
- 4. Subjects with a significant protocol deviation impacting baseline blood pressure.
- 5. Subjects with compliance outside of the range 70%-130%.
- 6. Subjects that took a prohibited medication potentially impacting baseline or Week 8 blood pressure.

Additional criteria may be identified prior to unblinding. If so, the additional criteria will be finalized and documented prior to database lock. Subjects who are included in the FAS but excluded from the PPS will be summarized for each criterion by treatment groups and overall. These subjects will also be presented in the listings.

The Ambulatory Blood Pressure Monitoring Set (ABPM Set) will consist of the subset of FAS subjects who received an ABPM recording at baseline. Subjects who have ABPM endpoints at both baseline and at least one post dose value will be included in all ABPM related summaries and analyses. Subjects who were randomized more than once are excluded from the ABPM Set.

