#### 7.10.1 Adverse Events

An AE is defined as any untoward medical occurrence in a clinical investigation subject that has been administered a pharmaceutical product, including placebo. It does not necessarily have to have a causal relationship with this treatment. AEs will be coded using MedDRA Version 20.0 MIXED.

A pretreatment event is defined as any untoward medical occurrence in a clinical investigation subject who has signed informed consent to participate in a study that occurs prior to administration of any study medication. It does not necessarily have to have a causal relationship with study participation. Pretreatment events will be summarized by SOC and PT.

Run-in AEs are defined as any untoward medical occurrence in a clinical investigation subject who has signed informed consent to participate in a study, which occurred on or after the first

dose of run-in placebo and prior to administration of double-blind study drug. Run-in AEs will be summarized by SOC and PT.

A treatment-emergent adverse event (TEAE) will be defined as any AE, regardless of relationship to study drug, that occurs after the first dose of double-blind study drug and no later than 14 days after the last dose of study drug for AEs, and no later than 30 days after the last dose of study drug for serious AEs. TEAEs will be summarized by SOC and PT.

AEs are recorded in the eCRF as being related or not related to study drug and study procedure. TEAEs that are recorded as related to study drug and/or study procedure will be summarized separately. TEAEs will also be summarized by intensity/severity (mild, moderate, severe). Serious TEAEs, TEAEs leading to study drug discontinuation and TEAEs leading to death will also be summarized.

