When calculating the frequency and percentage of subjects who reported TEAEs, a subject will be counted only once for each SOC or PT when multiple TEAEs are coded to the same SOC or PT. Thus, if a subject has two distinct AEs, each of which corresponds to a distinct PT but both of which correspond to the same SOC, then that subject will be counted once at that SOC subject-count summary level and once at each of the two PT subject-count summary levels. For the intensity summaries, if a subject reports multiple TEAEs coded to the same SOC or PT, then the TEAE with maximum intensity will be included in the summary. For the relationship summaries, if a subject reports multiple TEAEs coded to the same SOC or PT then the TEAE related to study drug will be included in the summary. If a TEAE is missing causality and/or intensity, then it will be assumed that the TEAE is related and/or severe in summary tables.

TEAEs will be summarized by treatment group, which will include the number and percentage of subjects as follows:

- Overview of Treatment-Emergent Adverse Events.
- Treatment-Emergent Adverse Events by SOC and PT (Overall and by Age groups: <45 years-old; 45-64 years old, inclusive; <65 years old; ≥65 years old; ≥75 years old).
- Treatment-Emergent Adverse Events by SOC.
- Treatment-Emergent Adverse Events by PT.
- Most Frequent (≥5% in any treatment arm) Treatment Emergent Adverse Events by SOC and PT (Overall and by Age groups: <45 years-old; 45-64 years old, inclusive; <65 years old; ≥65 years old; ≥75 years old).
- Most Frequent (≥5% in any treatment arm) Non-Serious Treatment Emergent Adverse Events by SOC and PT.
- Drug-Related Treatment-Emergent Adverse Events by SOC and PT (Overall and by Age groups: <45 years-old; 45-64 years old, inclusive; <65 years old; ≥65 years old; ≥75 years old).
- Intensity of Treatment-Emergent Adverse Events by SOC and PT

- Intensity of Drug-Related Treatment-Emergent Adverse Events by SOC and PT.
- Procedure-Related Treatment-Emergent Adverse Events by SOC and PT
- Treatment-Emergent Adverse Events Leading to Study Drug Discontinuation by SOC and PT
- Serious Treatment-Emergent Adverse Events by SOC and PT.
- Pretreatment Adverse Events by SOC and PT.
- Run-in Adverse Events by SOC and PT.

Subject mappings will be presented by SOC and PT for the summary of TEAEs, serious TEAEs and TEAEs leading to the discontinuation of study drug.

All AEs will be listed by site and subject number.

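### Read literally, the SAP's pretreatment-event and run-in AE tables leave out everyone who left before double-blind dosing

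*SAP*

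**What the plan says.** SAP 7.10 sets the population in one sentence: "All safety summaries will be based on the Safety Analysis Set". The next sentence reads "The safety analysis will use OC data and be restricted to descriptive statistics unless otherwise specified"; its exception clause concerns the data type and the use of descriptive statistics, not the population.

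SAP 7.3 defines the set: "The Safety Analysis Set will consist of all subjects who received at least one dose of double-blind study medication". Protocol 13.1.1 agrees: "All subjects who receive at least 1 dose of double-blind study medication". A dose of single-blind placebo alone does not qualify.

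SAP 7.10.1 plans two summaries of events before double-blind treatment: "Pretreatment events will be summarized by SOC and PT" and "Run-in AEs will be summarized by SOC and PT". Both reappear in that section's table list, the second as "Run-in Adverse Events by SOC and PT". The list is introduced as being summarised by treatment group. Neither table is given its own population.

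SAP 7.10.1 nevertheless defines both event types for any subject who has given consent. Protocol 10.2.1.1 collects pretreatment events until a subject who never reaches placebo discontinues, and collects AEs from the first placebo dose. Protocol 12.1 requires a case report form for everyone who signs consent.

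**The concern.** The two tables describe the time before double-blind dosing, but their population is fixed by having reached double-blind dosing. A subject who had an event off therapy or on placebo, and left because of it, cannot be counted in the table for that period.

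The selection is unlikely to be neutral. Randomisation requires a Day 1 sitting SBP of 150 to 180 mm Hg and a DBP not above 110 mm Hg (Protocol 7.1 and 7.2). Protocol 7.5 has subjects above 180 systolic or 110 diastolic re-measured and considered for withdrawal. Those whose pressure rises most off therapy are therefore among those filtered out. The tables would describe subjects who came through, and would tend to understate how often events occurred among all who were exposed.

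At stake is the completeness of two descriptive safety tables. SAP 7.10.1 also tabulates serious events only when they are treatment-emergent, so serious pretreatment and run-in events have no summary of their own.

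**Working it through.** The plan states no figure on this point, so there is none to reproduce. The check is one of set membership.

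1. Population of both tables = Safety Analysis Set (SAP 7.10).
2. Safety Analysis Set = at least one double-blind dose, excluding subjects randomised more than once (SAP 7.3).
3. A subject whose participation ends in screening, washout or placebo run-in takes no double-blind dose.
4. That subject is outside the set, and so outside both tables. The share of events that ended participation before double-blind dosing and are shown in these tables is 0, whatever the failure rate.

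The result by type of subject:

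| Subject | Pretreatment-event table | Run-in AE table | AE listing (SAP 7.10.1) | Disposition (SAP 7.4) |
|---|---|---|---|---|
| Left before first placebo dose | omitted | no such events, by definition | listed | counted by primary reason |
| Left during placebo run-in | omitted | omitted | listed | counted by primary reason |
| Randomised, never dosed | omitted | omitted | listed | counted as randomised but not treated |
| Randomised once and dosed | included | included | listed | counted by treatment |

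Two further checks:

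- *Is another population available?* SAP 7.3 defines the Randomized, Safety, Full Analysis, Per Protocol and ABPM sets. None contains a subject who was never randomised. The table list is by treatment group, and such a subject has no group. A programmer following the SAP has no alternative to the Safety Analysis Set.
- *Does the pretreatment table cover time off therapy?* Washout starts on Day -21, or on Day -28 for two named drugs, and placebo starts on Day -14. For subjects who need washout, 21 - 14 = 7 or 28 - 14 = 14 days of it precede placebo and fall under the pretreatment definition. The rest of washout coincides with run-in. Subjects not on treatment have no such interval.

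**The case against.** Several counter-arguments have force.

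- *The events are not lost.* SAP 7.10.1 lists all AEs by site and subject, with no limit to the Safety Analysis Set, and labels pretreatment events as adverse events in its table titles. Protocol 2.0 also puts all safety assessments in listings. SAP 7.4 counts screen and run-in failures by primary reason, with pretreatment event/AE as one category. Serious pretreatment events are handled as SAEs and reported within 24 hours (Protocol 10.1.4 and 10.2.2). This stands, and it limits the point to the two tables. A listing has no incidence or denominator, however, and disposition gives one reason per subject without SOC or PT.
- *A wider population may have been intended.* The event definitions refer to consent, SAP 7.3 speaks of routine safety analyses, and Protocol 13.1.4 allows exceptions. That is plausible, but neither document writes an exception for these tables.
- *Washout risk is not an objective.* The safety objective compares TAK-491 with valsartan. True, and it keeps the priority modest. But the SAP chose to plan these tables, and they should cover the period they name.
- *AE tables will not capture every exit.* Protocol 10.1.3 says insufficient response is not an AE, so exits for high pressure may be recorded only as failed entry criteria. True; re-basing recovers recorded events only.

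Stronger readings are tempting but unsupported. A reader might infer that the sponsor's safety case for washout rests on these tables, because Protocol 6.2 states: "This short-term washout/placebo treatment period is not associated with increased risk of major irreversible cardiovascular events". That statement cites external references and covers one class of event; it does not draw on this trial's data. A reader might also infer that all screen failures are missing from the run-in table. Those who took no placebo have no run-in events, and because washout should not begin until eligibility is verified (Protocol 6.1 and 9.3.2), many would never have stopped therapy.

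**Conclusion.** The point holds on the text. A stated rule, not a missing detail, restricts the two tables to subjects who later took double-blind drug. Pretreatment events in subjects who left earlier, and run-in events in run-in failures, are absent from them but still appear in the listing and, as reason counts, in disposition.

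The number affected cannot be derived, because the documents give no screen-failure, run-in-failure or event rate. A count could be built by assumption. With 600 randomised and run-in failure of 20% to 40%, entrants are 600/0.8 = 750 to 600/0.6 = 1000, so 150 to 400 are outside the tables. If 0.5% to 2% of entrants stopped for an AE, that is 750 × 0.005 ≈ 4 to 1000 × 0.02 = 20 subjects. Both ranges are assumed, and most of the 150 to 400 might have had no event. The conclusion does not rest on these figures and they should not be quoted as its size.

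The TEAE tables, the treatment comparison and the primary analysis are unaffected. This is an inexpensive improvement to pre-randomisation safety reporting, worth making before database lock.

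**What to change.** In SAP 7.10, exempt the pretreatment-event and run-in AE tables from the Safety Analysis Set rule and name a population for each:

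- **Run-in AEs:** all subjects who took at least one dose of single-blind placebo.
- **Pretreatment events:** all subjects who signed consent, with those who required washout also shown separately. Without that split, subjects who never stopped therapy would dilute the rate.
- **Columns:** overall, and split by whether the subject later took double-blind drug. In the SAP 7.10.1 table list, take these two tables out from under the by-treatment-group heading.
- **Flags:** within each table, mark serious events and events leading to discontinuation.

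Add the two populations to SAP 7.3, and keep the Safety Analysis Set for TEAEs.

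The cost is a short SAP wording change and minor extra programming for two descriptive tables. The data are already collected, no study procedure changes, and no inferential analysis is touched.

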#### 7.10.1 Adverse Events

An AE is defined as any untoward medical occurrence in a clinical investigation subject that has been administered a pharmaceutical product, including placebo. It does not necessarily have to have a causal relationship with this treatment. AEs will be coded using MedDRA Version 20.0 MIXED.

A pretreatment event is defined as any untoward medical occurrence in a clinical investigation subject who has signed informed consent to participate in a study that occurs prior to administration of any study medication. It does not necessarily have to have a causal relationship with study participation. Pretreatment events will be summarized by SOC and PT.

Run-in AEs are defined as any untoward medical occurrence in a clinical investigation subject who has signed informed consent to participate in a study, which occurred on or after the first

dose of run-in placebo and prior to administration of double-blind study drug. Run-in AEs will be summarized by SOC and PT.

A treatment-emergent adverse event (TEAE) will be defined as any AE, regardless of relationship to study drug, that occurs after the first dose of double-blind study drug and no later than 14 days after the last dose of study drug for AEs, and no later than 30 days after the last dose of study drug for serious AEs. TEAEs will be summarized by SOC and PT.

AEs are recorded in the eCRF as being related or not related to study drug and study procedure. TEAEs that are recorded as related to study drug and/or study procedure will be summarized separately. TEAEs will also be summarized by intensity/severity (mild, moderate, severe). Serious TEAEs, TEAEs leading to study drug discontinuation and TEAEs leading to death will also be summarized.

When calculating the frequency and percentage of subjects who reported TEAEs, a subject will be counted only once for each SOC or PT when multiple TEAEs are coded to the same SOC or PT. Thus, if a subject has two distinct AEs, each of which corresponds to a distinct PT but both of which correspond to the same SOC, then that subject will be counted once at that SOC subject-count summary level and once at each of the two PT subject-count summary levels. For the intensity summaries, if a subject reports multiple TEAEs coded to the same SOC or PT, then the TEAE with maximum intensity will be included in the summary. For the relationship summaries, if a subject reports multiple TEAEs coded to the same SOC or PT then the TEAE related to study drug will be included in the summary. If a TEAE is missing causality and/or intensity, then it will be assumed that the TEAE is related and/or severe in summary tables.

TEAEs will be summarized by treatment group, which will include the number and percentage of subjects as follows:

- Overview of Treatment-Emergent Adverse Events.
- Treatment-Emergent Adverse Events by SOC and PT (Overall and by Age groups: <45 years-old; 45-64 years old, inclusive; <65 years old; ≥65 years old; ≥75 years old).
- Treatment-Emergent Adverse Events by SOC.
- Treatment-Emergent Adverse Events by PT.
- Most Frequent (≥5% in any treatment arm) Treatment Emergent Adverse Events by SOC and PT (Overall and by Age groups: <45 years-old; 45-64 years old, inclusive; <65 years old; ≥65 years old; ≥75 years old).
- Most Frequent (≥5% in any treatment arm) Non-Serious Treatment Emergent Adverse Events by SOC and PT.
- Drug-Related Treatment-Emergent Adverse Events by SOC and PT (Overall and by Age groups: <45 years-old; 45-64 years old, inclusive; <65 years old; ≥65 years old; ≥75 years old).
- Intensity of Treatment-Emergent Adverse Events by SOC and PT

- Intensity of Drug-Related Treatment-Emergent Adverse Events by SOC and PT.
- Procedure-Related Treatment-Emergent Adverse Events by SOC and PT
- Treatment-Emergent Adverse Events Leading to Study Drug Discontinuation by SOC and PT
- Serious Treatment-Emergent Adverse Events by SOC and PT.
- Pretreatment Adverse Events by SOC and PT.
- Run-in Adverse Events by SOC and PT.

Subject mappings will be presented by SOC and PT for the summary of TEAEs, serious TEAEs and TEAEs leading to the discontinuation of study drug.

All AEs will be listed by site and subject number.

## 7.10.2 Clinical Laboratory Evaluations

Clinical laboratory tests will be assessed using the Safety Analysis Set and will be presented using System International (SI) units unless otherwise stated. Refer to Table 4.a for the schedule of measurements for clinical laboratory tests and to Table 7.b for a list of all clinical laboratory tests. Clinical laboratory data will be presented by subject and no inferential statistics will be presented.

The central laboratory will perform laboratory tests for hematology, serum chemistry, urinalysis, lipid panel, other screening/safety parameters and other tests listed in Table 7.b. Only data obtained within 7 days of the last dose of study drug will be included in the summaries. All data will be presented in the listings.

**Table 7.b** Clinical Laboratory Tests

Hematology	Serum Chemist	ry	Urinalysis			
Hemoglobin	Albumin		Specific gravity			
Hematocrit	Alanine aminotra	ansferase	pН			
Platelet count	Alkaline phospha	atase				
Red blood cell count	Aspartate aminor	transferase	Qualitative			
White blood cell count with	Bicarbonate		Protein			
differential	Bilirubin, total		Blood			
	Bilirubin, direct	(only if total is above ULN)	Ketones			
	Blood urea nitro	gen	Bilirubin			
	Calcium		Glucose			
	Chloride					
	Creatinine		Microscopy			
	Creatine kinase		Red Blood Cells			
	γ-Glutamyl trans	ferase	White Blood Cells			
	Glucose (serum)					
	Magnesium					
	Potassium					
	Protein, total					
	Sodium					
	Uric Acid					
	High-density lipoprotein cholesterol					
		protein cholesterol				
	Total cholesterol					
	Triglycerides					
Other						
HbA1c		Urine albumin				
Female subjects of childbearing p	otential only:	Urine creatinine				
Serum human chorionic gonadotr		Albumin: creatinine ratio				
Urine hCG for pregnancy (a)		eGFR				
		Plasma renin concentration a	and activity			
		Plasma and urine aldosteron	e			

(a) Urine hCG will be performed at the site on Day 1 (Visit 5) prior to randomization.

The following summaries of hematology, serum chemistry, urinalysis lab tests, lipid panel, and other will be presented for each scheduled time point (each visit and final visit):

Descriptive statistics (n, mean, SD, median, minimum, and maximum) by treatment group for the observed and change from baseline laboratory test values will be based on a single data value selected according to the window convention described in Table 7.a. Note that qualitative urinallysis parameters will only be listed.

Shifts in laboratory test values will be presented as cross-tabulations (baseline versus each post-baseline visit) of numbers of subjects with low, normal and high values relative to the normal range used at the central laboratory. Marginal totals will be provided for the baseline visit (e.g. total number of subjects with low, normal and high values at baseline) for each treatment group. Shifts from normal at baseline to high at visit (as well as normal to low) will be supplemented with the percentage (n in shift category/total normal at baseline). This classification will be based on the low, normal and high alert flags reported by the central laboratory. If a subject has

multiple values within a particular visit window, the most abnormal result will be used for summary. All clinical laboratory tests with reference ranges will be included in the shift summary.

Subjects with markedly abnormal values (MAV), identified by the criteria in Appendix A, for laboratory tests will be tabulated. If a subject has multiple values within a particular visit window, the most abnormal result will be used for summary. MAV tables will include all laboratory parameters with available MAV criteria.

The number and percentage of subjects with one or more post-baseline serum creatinine level  $\geq 1.3 \times$  baseline AND >upper limit of normal (ULN) (e.g., 30% creatinine elevation) and  $\geq 1.5 \times$  baseline AND >ULN (e.g., 50% creatinine elevation) will be summarized by visit. Subjects meeting these criteria at any post dose visits and remain elevated at the final visit will also be summarized and listed. The number and percentage of subjects with consecutive elevations will also be determined. The relationship between the change of creatinine and change of clinic BP may be assessed.

Listings of all clinical safety laboratory data will be provided by site and subject number. Listings will be produced for hematology, serum chemistry and urinalysis categories separately. Laboratory data outside of the normal reference ranges will be indicated in the listings. A listing of subjects with MAVs will be provided.

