#### 7.10.4 12-Lead ECGs

ECG data will be summarized using the Safety Analysis Set. The ECG endpoints include Heart Rate (beats/minute), RR interval (msec), PR interval (msec), QT interval (msec) and QRS interval (msec). Missing values of RR will be imputed as RR(msec) = 1000\*(60/HR). The

corrected QT interval will be computed using both Bazett's (QTcB = QT/RR1/2) and Fridericia's (QTcF = QT/RR1/3) formulas, where RR is presented in seconds. The QTc intervals computed by both methods will be summarized along with other vital signs parameters. No decimal place will be presented in the derived dataset and TLF outputs.

Descriptive statistics (n, mean, SD, median, minimum and maximum values) will be used to summarize 12-lead ECG values at Baseline, Week 8 or final visit and change from Baseline to Week 8 or final visit by treatment group.

The number and percentage of subjects with an increase  $\ge 30$  and  $\ge 60$  msec from Baseline in QTc interval will be tabulated as well as a tabulation of subjects with a post-baseline value > 500 msec and an increase  $\ge 60$  msec from baseline.

Overall ECG interpretation category (normal, not clinically significant abnormal, clinically significant abnormal) will be collected on the eCRF according to the scheduled measurements. Shifts in ECG interpretation will be presented as cross-tabulations of numbers of subjects with normal, not clinically significant abnormal, and clinically significant abnormal ECG interpretation results (and will include categories for missing and totals). Marginal totals will be provided for the baseline visit (e.g. total number of subjects in each category at baseline) for each treatment group. Percentage will also be provided.

Shifts in QTc intervals between Baseline and Week 8 will also be tabulated based on the value categories listed below:

- Females:  $\leq 450$ , > 450 to 470, > 470 to 500 and > 500 msec.
- Males:  $\leq 430$ ,  $\geq 430$  to 450,  $\geq 450$  to 500 and  $\geq 500$  msec.

Only data obtained within 7 days of the last dose of study drug will be included in the summaries. No inferential statistics will be presented. All ECG data will be presented in the data listings.

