## Urinalysis

Parameter	Low Abnormal	High Abnormal	
Blood		≥1+	
Glucose		≥1+	
Ketones		≥2+	
Casts		Any	
Microscopic RBCs*		≥5/hpf	
Microscopic WBC		$\geq$ 20/hpf	
рН	≤4	≥8	
Protein		≥1+	
Specific Gravity			

Hpf=high power field, RBC=red blood cell, WBC=white blood cell.

\* Markedly abnormal if repeated values both meet the criteria; e.g., if two values are greater than or equal to 5/hpf within 30 days of one another.

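### Markedly abnormal laboratory values are tabulated without regard to baseline, so some rows can mix new onset with persistence; a split by baseline status is a cheap, minor improvement

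*SAP*

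**What the plan says.** SAP 7.10.2 plans a table of markedly abnormal values (MAVs): "Subjects with markedly abnormal values (MAV), identified by the criteria in Appendix A, for laboratory tests will be tabulated". Where a visit window holds several values, the most abnormal one is used. The scope is wide: "MAV tables will include all laboratory parameters with available MAV criteria". The limits in SAP Appendix A are fixed values or multiples of the reference limits, with no change-from-baseline element. Protocol 13.1.4.2 asks for the number and percentage of subjects with MAVs and also sets no baseline condition.

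Elsewhere the SAP does take baseline into account:

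- **Creatinine (7.10.2).** "The number and percentage of subjects with one or more post-baseline serum creatinine level" at least 1.3 or 1.5 times baseline and above the upper limit of normal (ULN) is summarised.
- **QTc (7.10.4).** There is a "tabulation of subjects with a post-baseline value > 500 msec and an increase" of at least 60 msec from baseline.
- **Shift tables (7.10.2).** Baseline is crossed with each visit, but by "numbers of subjects with low, normal and high values relative to the normal range used at the central laboratory".

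For microscopic red cells, Appendix A (Urinalysis) requires repeated values, for example "if two values are greater than or equal to 5/hpf within 30 days of one another". It does not say whether both must come after the first dose.

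**The concern.** A safety reader usually wants to know from an MAV table how many subjects became markedly abnormal on treatment. Without a baseline condition, a subject past the limit on Day 1 and still past it at Week 4 counts the same as one who crossed it after dosing. The sentence on MAVs does not even restrict the count to post-baseline values, although the creatinine rule in the same section does.

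The shift tables do not supply the missing split where the MAV limit lies beyond the normal range. A subject who goes from moderately high to markedly high appears only as high to high, as does one who was markedly high throughout.

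Where baseline MAVs are not rare, the percentages rise, the ratio between arms is pulled towards 1, and the comparison becomes noisier. For microscopic red cells there is a further gap: a pre-dose value may complete the pair that defines an on-treatment abnormality.

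**Working it through.** **1. Which rows can be affected**

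| Test | Entry limit (Protocol 7.1, 7.2) | MAV limit (SAP Appendix A) | Consequence |
|---|---|---|---|
| ALT, AST | excluded above 2.5 × ULN at Screening | above 3 × ULN | near zero at baseline |
| Potassium, high | excluded above the normal range at Screening | above 6.0 mmol/L | near zero at baseline |
| Creatinine | eGFR below 30 excluded | above 177 µmol/L | separate baseline-relative rule exists |
| BUN | inclusion 6; partly exclusion 7 (eGFR below 30) | above 10.7 mmol/L | baseline MAV possible |
| GGT | inclusion 6; partly exclusion 12 (active liver disease, jaundice) | above 3 × ULN | baseline MAV possible |
| Uric acid, CK | inclusion 6 only | above 773 µmol/L; above 5 × ULN | baseline MAV possible |
| Urine red cells, white cells, pH | inclusion 6 only | ≥5/hpf; ≥20/hpf; ≤4 or ≥8 | baseline MAV possible |

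Inclusion 6 admits results outside the reference range if the investigator judges them not clinically significant. That is a limit, but a discretionary one.

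**2. Size**

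The plan states no MAV rate, so there is no figure to reproduce. All rates below are assumptions for one row at one visit, with 200 per arm (Protocol 8.1.3).

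Row percentage = p·s + (1 − p)·q, where p is baseline prevalence, s is the probability that a baseline MAV persists, and q is the new MAV rate among subjects not past the limit at baseline (4% vs 2%).

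With s = 0.5 in both arms:

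| p | Row reads | Difference (points) | Ratio |
|---|---|---|---|
| 0 | 4.0% vs 2.0% | 2.0 | 2.0 |
| 2% | 4.9% vs 3.0% | 2.0 | 1.66 |
| 5% | 6.3% vs 4.4% | 1.9 | 1.43 |
| 10% | 8.6% vs 6.8% | 1.8 | 1.26 |
| 15% | 10.9% vs 9.2% | 1.7 | 1.18 |

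Example at p = 10%: 0.10 × 0.5 + 0.90 × 0.04 = 0.086, and 0.10 × 0.5 + 0.90 × 0.02 = 0.068. After the split, the row for subjects not past the limit at baseline shows 4% vs 2% at every p.

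Varying equal persistence at p = 10% from s = 0.25 (6.1% vs 4.3%) to s = 1 (13.6% vs 11.8%) moves the ratio from 1.42 to 1.15. The difference stays at 1.8 points.

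With unequal persistence at p = 10%, 40% vs 60% gives 7.6% vs 7.8% (difference −0.2), and 60% vs 40% gives 9.6% vs 5.8% (difference 3.8).

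Noise at p = 10%, s = 0.5: SE = √(0.086 × 0.914/200 + 0.068 × 0.932/200) = 2.7 points. After the split, with 180 per arm not past the limit, SE = √(0.04 × 0.96/180 + 0.02 × 0.98/180) = 1.8 points. This only describes precision; the SAP plans no inference here.

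**3. Microscopic red cells**

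This check needs no prevalence assumption. Urinalysis is scheduled on Day 1 and at Weeks 2, 4 and 8 (Protocol Appendix A, ±2 days after Day 1). The scheduled days are 1, 14, 28 and 56 (SAP Table 7.a).

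| Pair | Interval (days) | Can fall within 30 days? |
|---|---|---|
| Day 1–Week 2 | 11–15 | always |
| Day 1–Week 4 | 25–29 | always |
| Week 2–Week 4 | 10–18 | always |
| Week 4–Week 8 | 24–32 | sometimes |
| Week 2–Week 8 | 38–46 | no |
| Day 1–Week 8 | 53–57 | no |

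Two of the four pairs that can qualify begin with a Day 1 value, which is the pre-dose baseline.

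**The case against.** The strongest case on the other side has four parts.

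- **Other outputs recover much of this.** Clinically significant laboratory changes are adverse events (Protocol 10.1.3), and those arising or worsening after dosing are tabulated as treatment-emergent (Protocol 13.1.4.1). MAVs are determined by study visit and SAP Table 7.a names Baseline as a visit, so a Baseline row is possible. Change-from-baseline summaries, shift tables and an MAV listing are also planned. This stands in part. Adverse events depend on the investigator's judgement, a Baseline row gives counts but not who persisted, and listings must be cross-classified by hand.
- **The size is assumed.** This stands. No document says that any Appendix A limit is passed by 5% or 10% of subjects at entry, and inclusion 6 works against extreme values.
- **Unequal persistence may be a real treatment effect.** This stands. A drug that changes how often an abnormality resolves is doing something that the all-subject total should show. The total should be kept and the −0.2 and 3.8 figures should not be called bias.
- **The tables are descriptive.** This stands. SAP 7.10.2 plans no inferential statistics for laboratory data.

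A reader might infer that dipstick protein, glucose and blood are the worst-affected rows, because their limit of 1+ is low. The documents do not settle this. SAP 7.10.2 also says: "Note that qualitative urinallysis parameters will only be listed". That may take these tests out of the MAV tables, or may apply only to the descriptive statistics beside which it stands. Microscopy and pH are outside the Qualitative sub-heading of SAP Table 7.b, so they remain on either reading.

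**Conclusion.** The point holds as a minor one. The MAV table cannot separate new from pre-existing marked abnormality. This can matter for rows such as BUN, GGT, uric acid, CK, urine microscopy and urine pH. It does not matter in practice for ALT, AST or high potassium, and creatinine is covered by its own rule.

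The size is unknown: nil where baseline MAVs are absent, and a ratio of about 1.26 in place of 2.0 at an assumed 10% prevalence with half persisting in both arms. The risk difference then barely changes. The red-cell pairing gap follows from the schedule alone, but how often it would count a subject is also unknown.

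Two stronger readings are tempting. One is that the safety comparison is biased or that a signal will be hidden. The documents do not support this: randomisation balances baseline MAVs on average, and no endpoint or decision rule uses the table. The other is that entry sets no limit on the affected tests. It does, through inclusion 6, and partly through exclusions 7 and 12 for BUN and GGT; the limit is simply not numeric for the test itself.

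**What to change.** In SAP 7.10.2, state that MAV tables show, by treatment group, the number and percentage of all subjects with a post-baseline MAV, followed by the same count by baseline status:

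- (a) criterion not met at baseline, with that group as denominator;
- (b) criterion met at baseline;
- (c) baseline missing.

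State that group (a) means not past the limit at the last pre-dose value. A subject past it at Screening but not on Day 1 falls in (a), so the row is not pure new onset.

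For microscopic red cells, require both values of the pair to be post-baseline, and define baseline status by the single baseline value being ≥5/hpf. State openly that this takes pairs straddling the first dose out of the red-cell total, and that one raised baseline value is enough to leave group (a) although it is not an MAV under the two-value rule.

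Whether the listing-only note on qualitative urinalysis also governs the MAV tables should go to the sponsor as a query.

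The cost is a few sentences, one baseline flag and up to three more rows per parameter. Day 1 laboratory data are already collected (Protocol 9.3.5) and baseline is already defined (SAP 7.1.3). The all-subject post-baseline total is kept for every other test. For red cells, the scheduled pairs left are Week 2–Week 4 and, when within 30 days, Week 4–Week 8, plus any unscheduled repeats; single values remain in the listings.
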